10.1 System and Compliance

The eCRF (study database); used to collect outcomes with the exception of the study intervention, will be a data capture system compliant with ICH-GCP (21 CRF Part 11) and MHRA guidelines for computerised systems. Isla platform data is transferred securely using state-of-the art SHA256 encryption in transit and at rest. Isla platform conforms with medical device regulations, General Data Protection Regulation (GDPR), NHS Digital Technologies Assessment Criteria (DTAC), the STARD-AI initiative and NICE Evidence Standards Framework for Digital Health.

Data will be collected from source documents or from participants directly and input into the eCRF (see section 10.2).

10.2 Source Data

Source documents are where data are first recorded, and from which participants' CRF data are obtained. These include but are not limited to: Data collected on the Isla care platform, hospital records and patient notes, patient questionnaires, and correspondence.

Outcome	Source
Demographic data	Medical case note review,
	Online survey administered via Dacima- will generate
Patient satisfaction	a report for storing
	Online Teams interview – will be transcribed for
Patient satisfaction	storing
	Online survey administered via Dacima – will generate
Staff satisfaction	a report for storing
	Online Teams interview – will be transcribed for
Staff satisfaction	storing
	Obtained through Isla or patient phone calls at 30 days
Wound infection data – infection status,	or surveillance records or medical case notes. Record
antibiotics	in medical case notes and eCRF
Intervention data – date of surgery and date	Obtained through Isla platform review. To be recorded
of infection diagnosis, adherence with	in eCRF (Dacima).
intervention (record per image with date and	
time), Isla submission completeness.	
	Obtained via a Telephone call, or medical case notes.
Wound infection data – readmissions, further	To be recorded in eCRF (Dacima) and medical case
surgery, GP visits, treatment	notes
	Baseline questionnaire at consent, repeated at 30 day
	online survey and 60 day phone call. To be recorded in
Quality of life	eCRF.
Consent	Consent form

eCRF entries will be considered source data for the following data - socioeconomic status (deprivation index & rural/urban location; compiled using post code), u owns smartphone, given a mobile, SSI is detected by clinicians using information available in Isla, image not sufficient quality, clinician requests another image, adverse events , adverse device effects, adherence with Isla submissions, number of images submitted, patient initiated submissions, clinician time to review images, grade of clinician reviewing images, number of attempts to phone patients, UKHSA phone call data, all health economic data obtained from patient or GP and quality of life score.

All documents will be stored safely in confidential conditions. On all trial-specific documents, other than the signed consent, the participant will be referred to by the trial participant number, not by name. Interviewees will also be referred to by their participant number on documents.

Investigators should keep records of all participating patients and all original signed informed consent forms. It is necessary for investigators to provide access to source document for monitoring and audit purposes to the Sponsor and any monitoring or regulatory authorities as deemed necessary.

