Trial Design:	 Randomisation: Mixed-block 1:1 randomisation stratified by site and sex managed by Derby CTSU. Intervention: (See flow chart) The intervention group will use the AI enabled platform with the new AI module for 30 days after surgery in addition to standard post-operative wound follow-up care for 60 days after surgery. Participants will be asked to submit images and information every 7 days post operatively, up until 30 days. Participants can also submit an image during the 30 days whenever they have a concern. Control: The control group will receive standard post-operative wound follow-up care for 60 days after surgery. Standard care, mapped during the economic scoping exercise in WP6 may include; out-patient appointments, advised to contact GP, or no follow-up. Neither of the two participating sites use Isla as their standard care. Data collection: We will develop online surveys for patients and staff focusing on safety, acceptability, quality of life, and barriers to underserved groups. Interviews with staff/patients exploring issues raised in surveys. Purposive sampling to include a range of ages, sex, ethnicities, physical abilities/carer dependence and socioeconomic status. Other tools include platform review, medical notes review and patient telephone calls at 30 and 60 days.
Trial Participants:	Patients ≥18 years old having coronary artery bypass graft (CABG) surgery.
Planner Number of Sites:	2
Planned Sample Size:	120 - National data shows a wound problem rate of 21% with a cardiac wound infection rate of 8%. A sample size of 120 patients should provide around 12 patients in each group with a wound problem of which 4-5 patients should have a wound infection. This is sufficient to inform feasibility, safety and acceptability data. Wound problems identified by the Isla platform include Discolouration, unexpected fluids/tissue, sutures/clips observed, incision after 14 days.
Treatment Duration:	Participants in the intervention group will be enrolled on Isla at hospital discharge or at 5 days after surgery for patients not discharged by day 5 post op. Patients will receive text requests via Isla up to 30 days after surgery.
Follow Up Duration:	Duration of follow up: Wound monitoring follow up is for 30 days after surgery (as per national guidelines) and we will follow up all patients for 60
	days after surgery to capture readmissions and further surgery data.

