11.2.3 Secondary Outcome Analysis

Safety outcomes. More detailed discussion about reasons for compliance/non-compliance will be explored in the staff surveys and interviews and the patient intervention group surveys and interviews (these will not form part of the statistical analysis). Survey data will be analysed using descriptive statistics, and qualitative data from the interviews (which will not form part of the statistical analysis) will analysed using thematic analysis.

Feasibility outcomes: access/barriers to participation and willingness of participants to be randomised, and attrition rates and time and resources required to conduct telephone assessments to patients and phone calls to GPs to collect antibiotic data. To contribute to sample sizes for a definitive trial - numberof wound problems/infections will be collected. Wound severity, wound-related hospital readmission, further surgery to treat wounds, prescribed wound treatments, prescribed antibiotics, clinic visits, GP visits will also be collected for the economic analysis (?).

Other secondary outcomes: number of photos received (per patient), number of requests (for images) complied with - intervention group only, number photos initiated by patients (intervention group only), number of follow-up requests.

For all secondary outcomes, continuous variables will be reported using descriptive methods such as means & 95% confidence intervals (95% CI). Categorical variables will be reported with frequencies & percentages.

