11.9 Health Economic Evaluation

An economic investigation was included as the provision of the intervention will involve additional upfront direct costs. The intervention is unlikely to be widely adopted unless it can be shown to be cost-effective. In order for the intervention to be cost effective, the initial upfront cost will need to be offset by savings later in the clinical pathway and/or deliver positive impacts on health outcomes. The economic investigation will comprise two stages: an initial scoping exercise and an economic evaluation on completion of the clinical study. The scoping exercise has been undertaken to inform

the design of this study. This involved a search for relevant economic evaluations and existing evidence base, the development of an early model and drafting of a health economic analysis plan. The economic evaluation will compare health outcomes and costs in the intervention and control arms using a probabilistic decision model. This will provide an estimate of the probability of cost-effectiveness of the intervention compared to standard of care and identify key parameters for cost-effectiveness for further investigation in a clinical trial. We will also explore the impact of different models of providing the intervention service.

12 MONITORING, AUDIT & INSPECTION Monitoring plan

The Investigator(s) must ensure that source documents and other documentation for this study are made available to study monitors, the REC or regulatory authority inspectors. Authorised representatives of the Sponsor and competent authority may visit the participating sites to conduct audits/ inspections.

Monitoring and source data verification will be conducted by the Derby CTSU according to the study monitoring plan. The extent and nature of monitoring will be determined by the study objectives, purpose, design, complexity, blinding, number of patients and sites, and endpoints.

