16.3 Appendix 3 – Amendment History

Amendment No.	Clinical investigation plan version no.	Date issued	Author(s) of changes	Details of changes made
1	V2.0	31 January 2024	JT JB	We have added 'quality of life throughout the protocol'. The statistician has added more detail to the protocol on reporting of continuous variable reporting (page 20) and sample size calculations (p34) and added the study progression criteria which were missing (p35).
			TL	We have added a sentence to clarify the wound healing information that will be obtained through the 30 day phone call and attached the UKHSA post-discharge questionnaire which is part of standard care.
2	V2.1	03 May 2024	VC	Updated the schedule of assessments to capture SF-6 at baseline and the modified UKHSA SSI post-discharge questionnaire (via the app and redacted version at Day 30)
			VC	Removed reference to SF-36
			VC	Baseline data content specified in detail in section 7.5 and removed the descriptive stats elements.
			VC	Note added re: changes in severity & serious criteria of adverse events
			DD	Legacy mentions of pregnancy in the eligibility criteria have been removed.
			JB	References to site-specific data collection have been removed from the 30-day phone assessment of wound healing and healthcare engagement. All patients will answer the same questionnaire during the 30-day phone assessment.

3	V2.2	19 March 2025	КС	Added: method of collecting information for processing participant
				reimbursement

Detail all clinical investigation plan amendments. Amendments must be submitted to the Sponsor for approval prior to submission to the REC committee or MHRA.

Page **47** of **47**

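### Isla is an extra route for detecting and dating wound infections that only the intervention arm has, so wound counts and diagnosis dates compared by arm are open to detection bias of unknown size

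*Protocol*

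**What the plan says.** The source table in section 10.2 gives infection status and antibiotics as "Obtained through Isla or patient phone calls at 30 days" or from surveillance records or case notes, to be written into the case notes and the eCRF. Date of infection diagnosis sits in a row labelled intervention data, with the source "Obtained through Isla platform review. To be recorded" in the eCRF. No other source is listed for that date. Among the items for which the eCRF itself is the source, the section lists "SSI is detected by clinicians using information available in Isla".

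Control patients do not have Isla. The Trial Summary says "Neither of the two participating sites use Isla as their standard care", and that standard care "may include; out-patient appointments, advised to contact GP, or no follow-up". Intervention patients receive the same standard care plus Isla requests at days 7, 14 and 21, and may send further images when concerned (Trial Summary; sections 4 and 7.6). Participants and wound-care staff know the allocation (section 7.4).

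Some collection is common to both arms. Everyone has a phone call at 30 and at 60 days and a case-note review at 60 days (sections 4 and 7.6). Appendix 1 schedules a healthcare treatment log and antibiotics at both time points. Appendix 3 says of the day-30 call: "All patients will answer the same questionnaire during the 30-day phone assessment".

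The counts have two stated uses. Section 11.2.3 says: "To contribute to sample sizes for a definitive trial - numberof wound problems/infections will be collected". Section 11.2.2 lists number and severity of wound problems and infections among the economic outcomes, and section 11.9 says: "The economic evaluation will compare health outcomes and costs in the intervention and control arms using a probabilistic decision model". Section 11.6 reports patient-based analyses by allocated treatment, and section 3.1 makes date of diagnosis a secondary outcome.

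**The concern.** An outcome that can be found by one more route in one arm will tend to be found more often there, and sooner, even if the wounds are the same. The extra route here is intensive: repeated photographs and questionnaires read by clinicians. The source list joins the routes with a simple alternative. It does not rank them, restrict the comparative count to shared ones, or provide for assessment blind to allocation.

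Section 2.0 anticipates fewer and less severe wound complications with the device. Better detection in the Isla arm works against seeing that, and could show a neutral or helpful intervention as one with more infections. A distorted count would then feed the cost-effectiveness comparison and the event rates for the next trial. Date of diagnosis is the sharpest case, because the only listed source does not exist for controls.

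**Working it through.** **1. Reproduce the plan's event counts.** Inputs are 60 patients per arm, a 21% wound problem rate and an 8% infection rate (section 11.1). 60 × 0.21 = 12.6 and 60 × 0.08 = 4.8. These match the Trial Summary's figures of around 12 wound problems and 4 to 5 infections per group.

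**2. Effect of unequal capture with no true effect.** Observed rate = true rate × proportion captured. With the same true rate in both arms, the true rate cancels and the spurious risk ratio is intervention capture ÷ control capture. The documents give neither. Setting intervention capture to 100% and *assuming* control capture of 70% to 90%:

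| Control capture (assumed) | Spurious risk ratio | Wound problems per 60, Isla v control | Infections per 60, Isla v control |
|---|---|---|---|
| 100% | 1.00 | 12.6 v 12.6 | 4.8 v 4.8 |
| 90% | 1 / 0.9 = 1.11 | 12.6 v 11.3 | 4.8 v 4.3 |
| 80% | 1 / 0.8 = 1.25 | 12.6 v 10.1 | 4.8 v 3.8 |
| 70% | 1 / 0.7 = 1.43 | 12.6 v 8.8 | 4.8 v 3.4 |

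From 90% down to 70%, this is a spurious difference of 2.1 to 6.3 percentage points for wound problems and 0.8 to 2.4 points for infections. Using one row for both outcomes also assumes that infections are missed as often as minor problems, which the documents do not support.

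**3. Compare with sampling error.** With equal detection and no effect, the approximate 95% range of the observed risk ratio is exp(±1.96 × √[2(1/e − 1/60)]), where e is the expected events per arm.
- Wound problems, e = 12.6: exp(±0.694), or 0.50 to 2.00.
- Infections, e = 4.8: exp(±1.213), or 0.30 to 3.4.

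The assumed bias of 1.11 to 1.43 lies inside both ranges.

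**4. Illustration for the definitive trial.** Assume 8% v 4% infections, 90% power and a two-sided 5% level. The usual two-proportion formula is n = [1.96√(2p̄(1−p̄)) + 1.2816√(p₁(1−p₁) + p₂(1−p₂))]² / (p₁ − p₂)², which gives 739 per arm with equal detection. At control capture of 90%, 80% or 70%:
- using only the control rate, with the risk ratio held at 0.5: 827, 936 or 1,077 per arm;
- using the observed rates of both arms: 1,083, 1,797 or 3,750 per arm.

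The protocol does not say which rates it would use, so these figures show only that the choice matters.

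**The case against.** The strongest reply is that section 10.2 lists source documents and is not a counting rule. How sources are combined could be settled in the SAP or in the health economic analysis plan that section 11.8 says has been prepared, and neither is at hand. That is fair as far as it goes, and it means that biased counting is not certain. But the protocol itself lists a source that one arm cannot have, and for diagnosis date it lists nothing else. Followed as written, that gives unequal detection, which is more than a detail left for later.

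Several stronger readings are tempting, and the documents do not support them:

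- A reader might infer that controls are followed only by one call at day 30. They also have the 60-day call, the 60-day case-note review and the treatment log at both times.
- A reader might infer that all the economic inputs are affected. Section 10.2 takes readmissions, further surgery, GP visits and treatment from phone calls or case notes, without Isla. The affected items are infection status, antibiotics and diagnosis date.
- A reader might infer that some flagged problems, such as retained sutures or clips, can be seen only in a photograph. Nothing says so; patients, GPs or clinics could notice and record them.
- A reader might infer that the definitive sample size will be wrong. Section 11.2.3 says only that the counts contribute. If only the control rate is used, over-counting in the Isla arm does not matter and under-capture in controls is what remains.

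Two further points stand and shape the remedy. Infection status is to be written into the case notes, so Isla detections will appear in a source that looks common to both arms. And care triggered by Isla is a real consequence of the intervention, so its costs must not be removed from the economic model.

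**Conclusion.** The concern holds as a risk of detection bias in between-arm wound problem and infection counts and in diagnosis dates. The likely direction is more and earlier events in the intervention arm. Isla adds to the shared calls and records and does not replace them, so the bias can be much reduced with data already planned.

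Its size cannot be computed from the documents. The range of 1.11 to 1.43 rests wholly on the assumed 70% to 90% relative capture and should not be read as an estimate. It is smaller than the sampling error at this sample size, but it would not shrink in a larger trial that kept the same sources. The precision-based sample size and the progression criteria (recruitment, adherence, completion) do not use wound counts and are unaffected.

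**What to change.** 1. Base the between-arm wound problem and infection count on the identical day-30 phone questionnaire, supplemented by the 60-day call and case-note review applied in the same way to both arms.
2. Record in the eCRF how each event was first detected (Isla or other). Report Isla-first detections in a separate intervention-only row, and show the comparative count with and without them, because Isla findings also reach the case notes.
3. Name a source for date of infection diagnosis that applies to control patients.
4. Use wound-related readmission or further surgery as the less detection-sensitive check, since their listed sources exclude Isla. Antibiotics will not serve, because they share the row that includes Isla.
5. Keep all real costs of Isla-triggered care in the economic model. Use the common-source event rates there as the base case or a sensitivity analysis, and use them for the definitive sample size.

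The cost is wording in section 10.2, the SAP and the health economic plan, plus one eCRF field building on the existing Isla-detection item; no new patient contact is needed. The downside is fewer events in the comparative count. Some residual bias will remain, because contact through Isla can influence both the notes and what patients recall on the calls.

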10.3 Data Workflow

The DCTSU Data Management (DM) team will design the database to capture the clinical data in accordance with the best principles of clinical data management and the relevant SOP on Case Report Form and Database Selection, Development & Release developed by Derby CTSU.

When data are entered into the EDC (by site staff, the participant or DCTSU staff), validation checks will be performed on the data to ensure accuracy and consistency according to the study Data Validation Plan. All data queries generated as a result of these checks will be available for resolution by the site online. After data entry is complete, all data queries have been resolved, any required coding is complete and all forms have been signed by the PI, the database will be locked and released for statistical analysis.

All clinical data will be collected, stored, processed, and archived in accordance with the Data Management Plan for this trial and in line with the relevant SOPs on Data Entry, Data Closeout Activities and Archiving developed by the Derby CTSU and any relevant legislation.

10.4 Data Access and Security

Direct access will be granted to authorised representatives from the Sponsor, Derby CTSU, host institution and the regulatory authorities to permit study-related monitoring, audits and inspections.

All documents will be stored safely in confidential conditions. With the exception of regulatory authorities, only authorised members of the study team will have access to source documents.

Access to the study database will be role-specific and password protected. DCTSU DM will control access, granting access to sites as recorded on the Delegation Log(s). The CI, PI, DCTSU staff and site staff will be given appropriate access & permissions dependent on their role.

Each participant will be assigned a participant ID for use on study forms, other study documents and the electronic database. The investigator and trial team will ensure that the participant's identity is protected at every stage of their participation within the trial. If any patient information needs to be sent to a third party the trial team will adhere to maintaining pseudo-anonymous participant parameters in correspondence.

Images from patients will be kept as source data and archived. Images will be made available for other research studies upon request. This will be made clear in the information given to patients and the consent form.

10.5 Archiving

At the end of the study, following completion of the end of study report, the study Sponsor will securely archive all centrally held study related documentation for a minimum of 10 years. At the end of the defined archive period arrangements for confidential destruction will be made. It is the responsibility of each PI to ensure that data and all essential documents relating to the study are retained securely for a minimum of 10 years after the end of study, and in accordance with national legislation. All archived documents must continue to be available for inspection by appropriate authorities upon request.

11.0 STATISTICS AND DATA ANALYSIS

11.1 Sample Size Calculation

This is a feasibility study and therefore, sample size calculations cannot be calculated as there are no current data which can be used as the basis of the calculations. The feasibility outcomes for this study are all binary outcomes, for which the widest confidence intervals will occur with a proportion of 0.5 (or 50%), therefore calculating a sample size for the confidence interval based on 50% give a "worst case" estimate.

Recruiting 60 patients for each treatment group into the trial (i.e. a total of 120 patients) will enable us to estimate the recruitment and drop-out rates with a 95% confidence interval of within +/- 10% even if the rates were 50% for these two feasibility outcomes (The 95% confidence interval for a sample size of 120 patients and 60 successes, i.e. 50% of patients recruited, or 50% of patients completing the study, is 41% to 59%). If the adherence to treatment rate was 50%, the adherence rate and 95% confidence interval could be estimated to within +/- 13% (the 95% confidence interval for 30 adherent patients out of 60, as this is only relevant for patients in the intervention group, is 37% to 63%). The sample size estimations were calculated using STATA V18 with command "cii proportions". In addition, national data shows a wound problem rate of 21% (our data shows 15%) with a cardiac wound infection rate of 8%.⁸ A sample size of 120 patients should have a wound infection. This is sufficient to inform feasibility, safety and acceptability data.

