11.2 Planned Recruitment Rate

We plan to recruit 120 patients over ten months, from sites that are expected to operate on at least 1,300 eligible patients over 10 months, which equates to a maximum recruitment rate of around 11%. This should be achievable as patient-facing data collection (survey x1, phone calls x2, and interview for subset of 20 participants) is not burdensome and an RCT looking at an App to monitor surgical wounds had 69% recruitment rate.⁹

Statistical Analysis

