11.2.2 Primary Outcome Analysis

Safety outcomes: quality of images received, assessed by clinicians at 30 days(a quality image is one that can be used to make a clinical decision). These will be reported using frequencies and percentages.

Acceptability outcomes: clinician and patient satisfaction using surveys and interviews at day 30. The interviews will investigate the acceptability of the intervention including attitude, burden, perceived effectiveness, ethicality, intervention coherence, opportunity costs and self-efficacy and will be analysed using qualitative methods. Will also collect acceptability of being involved as a study participant. Survey variables that are continuous will be reported with means & 95% confidence intervals (95% CI), if shown to be normally distributed, using a normality plot, otherwise will be reported with medians & Interquartile Ranges (IQR). The categorical variables will be reported with frequencies & percentages.

Feasibility outcomes: recruitment rate, adherence with the module (intervention group only), loss to follow-up. Adherence will be reported as the number and percentage of adherent patients in the intervention group. To be adherent a patient needs to submit one photo with a completed questionnaire within the 30 day period. This will be compared with the progression criteria defined below. The definitive study will proceed (or not) based on these outcomes. The number and

percentage of eligible patients recruited to the study will be reported. All feasibility outcomes will be reported with 95% confidence intervals.

Progression criteria

Criteria:	Do not proceed	Proceed with changes	Proceed		
Recruitment	<10% of eligible patients	between 10% and <25% of	at least 25% of eligible		
	consent	eligible patients consent	patients consent		
Adherence with	<40% of intervention	between 40% and <80% of	at least 80% of		
the module	patients submit one or	intervention patients	intervention patients		
	more images	submit one or more images	submit one or more		
			images		
Loss to follow-up	<10% of intervention	between 10% and <60% of	at least 60% of		
	patients complete the	intervention patients	intervention patients		
	study	complete the study	complete the study		

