11.6 Analysis Groups

Recruitment rate (including access and barriers to recruitment and willingness to be randomised) will be assessed as a percentage of all eligible patients, regardless of treatment allocation. Patients who were consented but not randomised will not be included in the recruitment rate. Adherence to the module will be assessed based on patients allocated to the intervention. Loss to follow-up will be assessed based on all randomised patients..

All other patient-based analyses will be reported based on allocated treatment, except for adverse events and adverse device events, which will be reported based on the treatment the patients received.

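### Section 11.1 gives the recruitment rate a confidence interval on the wrong denominator; the slip is conservative and leaves the sample size and analysis unchanged

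*Protocol*

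**What the plan says.** Section 11.1 of the protocol states the planned size and the precision it is meant to buy. With 60 patients in each group, 120 in all, the team expects to "estimate the recruitment and drop-out rates with a 95% confidence interval of within +/- 10" percentage points, including at a rate of one half. A single interval serves both outcomes. Its basis is given as "The 95% confidence interval for a sample size of 120 patients and 60 successes, i.e. 50% of patients recruited". The section then applies the same counts to completion of the study and prints limits of 41% and 59%. For adherence the same section changes the denominator to the 60 intervention patients and gives 37% to 63%.

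The definition of the recruitment rate is elsewhere. Section 11.6 says that it "will be assessed as a percentage of all eligible patients, regardless of treatment allocation", and section 11.2.2 says that "The number and percentage of eligible patients recruited to the study will be reported". The progression table in 11.2.2 also works in percentages of eligible patients, with a stop limit below 10% and a proceed limit of at least 25%. Section 11.6 bases loss to follow-up on all randomised patients.

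On numbers, section 11.2 says "We plan to recruit 120 patients over ten months". The sites are forecast to operate on no fewer than 1,300 eligible patients in that time, and the section describes this as a maximum rate of around 11%.

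**The concern.** The 120 patients are those recruited. In a rate defined as recruited over eligible, they are the numerator. Section 11.1 uses them as the denominator. Read literally, 60 successes out of 120 describes a study that found 120 eligible patients and recruited 60. With 120 recruited, a 50% rate means 240 eligible patients.

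The same interval is correct for completion, because there the 120 randomised patients are the denominator. The section also changes the denominator for adherence, so it does match denominators to outcomes in general but not for recruitment.

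Recruitment is a primary feasibility outcome and one of three progression criteria. Section 11.1 holds the protocol's only statement of how precisely it will be estimated. That statement uses a denominator the analysis will not use and a rate (50%) well above both progression limits, so it does not tell the reader how precise the estimate will be where the decision is made.

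**Working it through.** **Inputs.** Recruited: 120 (section 11.1). Recruitment denominator: all eligible patients (11.2.2 and 11.6). Forecast eligible: at least 1,300 (11.2). Limits: 10% and 25% (11.2.2). The eligible counts 240, 480 and 1,200 are illustrative; each is 120 divided by the rate of interest (120/0.50, 120/0.25, 120/0.10).

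**Method.** Exact (Clopper-Pearson) two-sided 95% interval for x out of n:
- lower limit = 2.5th percentile of Beta(x, n − x + 1)
- upper limit = 97.5th percentile of Beta(x + 1, n − x)

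I take this to be the method behind the Stata command that 11.1 cites. The half-width is half the distance between the limits.

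**Reproducing the plan's figures.**
- 60/120: exact 40.7% to 59.3%, half-width 9.3 points. Wald gives 41.1% to 58.9% and Wilson 41.2% to 58.8%. All round to the printed 41% to 59%.
- 30/60: exact 36.8% to 63.2%, which rounds to the printed 37% to 63%.

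So the arithmetic is right for the counts entered. The fault is in which counts were entered for recruitment.

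**Recruitment on its defined denominator, x = 120.**

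| Eligible | Rate | Exact 95% interval | Half-width (points) |
|---|---|---|---|
| 240 | 50% | 43.5% to 56.5% | 6.5 |
| 480 | 25% (proceed limit) | 21.2% to 29.1% | 4.0 |
| 1,200 | 10% (stop limit) | 8.4% to 11.8% | 1.7 |
| 1,300 | 9.2% (forecast minimum) | 7.7% to 10.9% | 1.6 |

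**Size of the error.** The fair comparison holds the rate fixed. At 50% it is 9.3/6.5 = 1.4.

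**Does the claim of within 10 points survive?** Yes. With 120 recruited and any larger number eligible, neither exact limit is ever more than about 7.5 points from the estimate; the widest case is near 166 eligible.

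**The planned rate.** 120/1,300 = 9.2%. A rate of 11% would need 120/0.11, or about 1,091 eligible patients, which is below the stated minimum. At exactly 1,300 eligible, the interval of 7.7% to 10.9% contains 10%.

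**The case against.** The strongest reply is that nothing downstream depends on the slip, and most of that stands.

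- **The bound holds.** Section 11.1 promises precision within 10 points and calls 50% the worst case. The eligible denominator cannot be smaller than 120, so the real interval is narrower than the printed one.
- **The size of 120 does not rest on recruitment.** The 60/120 interval is correct for completion, and the wider 30/60 interval for adherence is also correct. With recruitment removed, the case for 120 is the same.
- **The analysis is already right.** Sections 11.2.2 and 11.6 fix the eligible denominator, and 11.2.2 requires 95% confidence intervals for all feasibility outcomes, so the correct interval will be reported whatever 11.1 says.

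Three stronger readings are tempting, and the protocol does not support them.

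- A reader might infer that the printed interval is about six times too wide (9.3 against 1.6). That sets a 50% rate beside a 9.2% rate, so much of the gap comes from the proportion and not from the denominator. At about 9.2% in both cases, 11/120 has a half-width of 5.6 points against 1.6, roughly 3.5 times. At the 50% rate that 11.1 uses, the factor is 1.4.
- A reader might infer that 11.1 conceals a conflict with the stop limit. The 1,300, the 11% and the 10% limit are all printed openly. How close the planned rate lies to the limit is a separate planning question, which correcting the denominator would not settle.
- A reader might infer that the true interval straddles 10%. That is conditional, since 1,300 is a forecast minimum. At 1,430 eligible, 120 recruited gives 7.0% to 9.95%, wholly below 10%; with fewer eligible, the rate rises.

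What does not yield to the reply is narrow: 11.1 attaches a specific interval to a primary outcome, and that interval is not the outcome's interval under the protocol's own definition.

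**Conclusion.** The point holds as a denominator error in one sentence, and its severity is minor to moderate. The interval of 41% to 59% describes completion among 120 randomised patients. For recruitment at 50% the exact interval is 43.5% to 56.5%. The error is on the safe side: it does not make the trial too small or alter any planned analysis or progression rule.

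It is still worth correcting, because recruitment feeds a go/no-go decision and the protocol's only precision figure for it is wrong as written. Restating it near the limits also shows that the 11% in section 11.2 does not follow from 120 and 1,300, and that at exactly 1,300 eligible the data could not separate the rate from 10%.

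This rests on two assumptions: that the full 120 are recruited, and that the intervals are exact binomial. The number eligible is not fixed by design, so every recruitment interval here is conditional on the count shown.

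**What to change.** In section 11.1, remove recruitment from the 60/120 sentence and keep 41% to 59% for completion or drop-out among the 120 randomised. Add a sentence on recruitment precision with all eligible patients as the denominator, to agree with section 11.6; patients approached would be a different rate. Use exact intervals:

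- 120/1,300 = 9.2% (7.7% to 10.9%), if exactly the forecast minimum is eligible
- 120/1,200 = 10% (8.4% to 11.8%), at the stop limit
- 120/480 = 25% (21.2% to 29.1%), at the proceed limit

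In section 11.2, reconcile the rate of around 11% with 120/1,300 = 9.2%, and note that at 1,300 eligible the interval includes the 10% limit.

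The cost is one paragraph in 11.1 and one figure in 11.2. The sample size, data collection and analysis do not change.
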